8.2.12. Urinalysis

Urinalysis will include analysis for pH, specific gravity, glucose, ketones, blood, protein, creatinine, urobilinogen, bilirubin, nitrite, and leukocyte esterase. These parameters will be measured at Screening/Baseline on Visit 1, Week 12 (Visit 2), Week 24 (Visit 3), Week 36 (Visit 4), Week 48 (Visit 5), Week 60 (Visit 6), Week 72 (Visit 7), Week 84 (Visit 8), Week 96 (Visit 9)

- End-of-Treatment/Premature Discontinuation), and at the Post-Treatment visit (4 weeks post discontinuation of study drug). These parameters will be analyzed by the central laboratory. Urine samples will also be collected and shipped to central laboratory for assessment of urine protein, creatinine, osmolality, and urinalysis. The Central Laboratory Manual should be consulted for collection, processing, and shipping details.

8.2.13. Renal Ultrasound

An ultrasound to examine the kidneys and collecting system will be performed at Screening/Baseline (Visit 1), Week 48 (Visit 5) and Week 96 (Visit 9 – End of Treatment/Premature Discontinuation) visit. The ultrasound examination will be performed according to local standards and a final interpretation and report will be provided by a local qualified expert. The findings will be captured in source documents and within the CRF.

A follow-up renal ultrasound may also be performed at any time during the study as clinically indicated at the discretion of the investigator. The PTC medical monitor must be informed via e-mail that an additional renal ultrasound was obtained and the serious adverse event reporting process should be followed, if applicable.

8.2.14. 12-Lead ECG

A 12-lead ECG will be obtained at Screening/Baseline (Visit 1), Week 48 (Visit 5), Week 96 (Visit 9 – End of Treatment/Premature Discontinuation) visit, and at the Post-Treatment Visit (4 weeks post discontinuation of study drug). The ECG will be performed and interpreted locally for clinical significance. The findings will be captured in source documents and with the CRF.

A follow-up ECG may also be performed at any time during the study as clinically indicated at the discretion of the investigator. The PTC medical monitor must be informed via e-mail that an additional ECG was obtained and the serious adverse event reporting process should be followed, if applicable.

8.2.15. Study Drug Administration

Patients should take study drug TID as described in Section 6.2.2 Study drug supply sufficient for each 12-week treatment period will be supplied to the patient at Screeing/Baseline (Visit 1), Week 12 (Visit 2), Week 24 (Visit 3), Week 36 (Visit 4), Week 48 (Visit 5), Week 60 (Visit 6), Week 72 (Visit 7), and Week 84 (Visit 8). Sufficient drug for 90 days (12 weeks + 6 days) will be provided at each of these visits so lessen the likelihood that patients will experience drug shortages due to inadvertent loss of some of the sachets or scheduling delays for return visits.

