The primary objective of this Phase 3 extension study will be to obtain long-term safety data to augment the overall safety database. The secondary objectives will be to augment the efficacy data collected in the double-blind study (PTC124-GD-021-CF).

Screening and baseline procedures are structured to avoid a gap in treatment between the double-blind study (PTC124-GD-021-CF) and this extension study. When possible, Screening/Baseline (Visit 1) for this extension study should occur on the same day as the End-of-Study visit for the double-blind study (PTC124-GD-021-CF). During the treatment period, study assessments will be performed at clinic visits at Week 12 and thereafter every 12 weeks until the end of the study.

Planned interim safety analyses will be conducted by an independent data monitoring committee (DMC). The first safety review will occur when ~ 100 patients have completed $\geq =36$ weeks of treatment. The second safety review will occur when ~ 100 patients have completed $\geq =72$ weeks of treatment.

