6.1.5. Return of Study Drug

Patients should return all remaining study drug (all unused sachets) to the study site at the end of each 12-week treatment period for inventory. The Subject Study Drug Accountability Log will serve as the source document for drug supply to the patients and will document the return of any unused drug for compliance assessments.

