6.2. Study Drug Treatment

6.2.1. Duration of Treatment

In this study, treatment will comprise continuous daily treatment with ataluren for up to 96 weeks (~2 years). This study may be further extended by amendment until either ataluren

becomes commercially available or the clinical development of ataluren in nmCF is discontinued.

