8. SCHEDULE OF EVENTS AND STUDY PARAMETERS

8.1. Schedule of Events

The proposed types and timing of data to be recorded are described in Table 3. Please see Section 8.2 for cross-referenced explanations of the study procedures described in the tables.

Study Period	Screening/ Treatment Per					Perio	bd		Post-Treatment	
Study Week (±7 days)	Day 1	12	24	36	48	60	72	84	End of Tx/ Premature D/C 96	4 Weeks Post-Tx
Visit	1	2	3	4	5	6	7	8	9	10
Informed consent	Х									
CFQ-R administration	Xa	Х	Х	Х	Х	Х	Х	Х	Х	
Vital signs	Xa	Х	Х	Х	Х	Х	Х	Х	Х	Х
Height	Xa	Х	Х	Х	Х	Х	Х	Х	Х	Х
Weight	Xa	Х	Х	Х	Х	Х	Х	Х	Х	Х
Physical examination	Xa				Х				Х	Х
Hematology	Xa	Х	Х	Х	Х	Х	Х	Х	Х	Х
Biochemistry	Xa	Х	Х	Х	Х	Х	Х	Х	Х	Х
Urinalysis	Xa	Х	Х	Х	Х	Х	Х	Х	Х	Х
Renal ultrasound	Xa				Х				Х	
12-lead ECG	Xa				Х				Х	Х
Study drug assignment	Х									
Drug dispensed	Х	Х	Х	Х	Х	Х	Х	Х		
Drug compliance		Х	Х	Х	Х	Х	Х	Х	Х	
Adverse events	Х	Х	Х	Х	Х	Х	Х	Х	Х	Х
Concomitant medication	Х	Х	Х	Х	Х	Х	Х	Х	Х	Х
Spirometry	Xa	Х	Х	Х	Х	Х	Х	Х	Х	Х
Respiratory event evaluation ^b	Xa	Х	Х	Х	Х	Х	Х	Х	Х	
P. aeruginosa in sputum	Xa	Х	Х	Х	Х	Х	Х	Х	Х	
Pharmacokinetics			Х		Х		Х		Х	

Table 3. Schedule of Events

^a Study procedure need not be performed if Day 1 is within 14 days of the end of study evaluations at Week 48 (Visit 8) of the preceding Phase 3 double-blind study (PTC124-GD-021-CF). If Day 1 is >14 days from the end of study visit, study procedure must be performed; however, it is not required to assess serum electrolytes, urine protein; urine creatinine ratio (spot sample), or urine blood (by dipstick).

^b Includes completion of the Respiratory Event Form.

° **Abbreviations**: D/C = discontinuation; ECG = electrocardiogram; F/U = follow up; Tx = treatment

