8.2.16. Study Drug Compliance

Study drug compliance will be assessed using a Subject Study Drug Accountability Log (to be completed by the investigational site pharmacist or delegate site staff), which will document the return of unused sachets for compliance assessments.

Patients or caregivers will return all unused sachets of study drug to the study site for full compliance assessments using the Subject Study Drug Accountability Log. Clinic staff will record the study drug dosing information including the actual clock time of each dose when the patient is dosed in the clinic.

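### The 90-day drug supply is shorter than the longest interval the ±7-day visit window allows (91 days to Week 12, up to 98 days later), so a patient within protocol can run short of ataluren just before a visit

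*Protocol*

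**What the plan says.** - **Supply.** Protocol 8.2.15 states "Sufficient drug for 90 days (12 weeks + 6 days) will be provided at each of these visits", meaning Visits 1 to 8. The stated purpose of the surplus is to "lessen the likelihood that patients will experience drug shortages due to inadvertent loss of some of the sachets or scheduling delays for return visits". Protocol 6.1.4 adds that enough drug is given at the start of each study period to cover that period.
- **Visits.** Protocol 1 sets "clinic visits at Week 12 and thereafter every 12 weeks until the end of the study". Table 3 (Protocol 8.1) labels its week row "Study Week (±7 days", so the window applies to every scheduled week.
- **Returns.** Protocol 6.1.5: "Patients should return all remaining study drug (all unused sachets) to the study site at the end of each 12-week treatment period for inventory". Protocol 8.2.16 repeats this: "Patients or caregivers will return all unused sachets of study drug to the study site for full compliance assessments". Neither section says whether counted sachets are handed back.
- **Intended exposure.** Protocol 6.2.1 describes uninterrupted daily dosing for up to 96 weeks.

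No section caps the number of days between consecutive visits or describes resupply between visits.

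**The concern.** One 6-day surplus has two jobs, lost sachets and late visits, yet it is smaller than the 7 days of lateness that the schedule treats as on time. A patient can attend every visit in window, lose nothing, and still have no drug, or not enough for every dose, in the last days of an interval.

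The timing matters more than the number of days. A shortfall always comes at the end of an interval, immediately before the visit at which safety laboratory values and spirometry are collected, and at Weeks 24, 48, 72 and 96 the pre-dose trough sample too. Laboratory abnormalities are part of the primary endpoint.

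The SAP would not separate such values out. SAP 5.2 uses scheduled visits without window mapping, and SAP 4.9 defines treatment duration regardless of interruptions. By-visit tables would therefore present them as ordinary on-treatment results. If the patient-years in SAP 4.10.1 were taken from that duration, the days without drug would also sit in the denominator of the exposure-adjusted event rates.

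**Working it through.** **Inputs.** Supply of 90 days (Protocol 8.2.15); visit spacing of 12 weeks = 84 days (Protocol 1); window of ±7 days (Table 3); kits of 120 sachets of one strength (Protocol 6.1.2).

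**1. The plan's own figure.** 12 × 7 + 6 = 90 days. This reproduces.

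**2. Longest in-window interval.**
- Day 1 to Week 12: Day 1 is the origin and has no early side, so 84 + 7 = 91 days. Shortfall 91 − 90 = 1 day.
- Each of the seven later intervals (Visit 2–3 to Visit 8–9), first visit 7 days early and next 7 days late: 84 + 14 = 98 days. Shortfall 98 − 90 = 8 days if nothing is carried over.
- A later interval whose first visit is on time and whose next is 7 days late: 91 days, 1 day short.

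**3. If returned sachets are handed back.** By the k-th visit after Day 1, cumulative supply is 90k days and the most that can be needed is 84k + 7. The shortfall is 7 − 6k: 1 day at k = 1, none from k = 2 on (before any losses).

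**4. How often, without carry-over.** Actual visit timing is not in the documents. As an illustration, assume whole-day deviations, uniform on −7 to +7 and independent between visits.
- First interval: only +7 exceeds 90 days, so 1/15 = 6.7%.
- Later intervals: let d be the second deviation minus the first. The interval exceeds 90 days when d ≥ 7. There are 15 − d pairs for each d, so 8 + 7 + … + 1 = 36 of 225 pairs = 16%.
- The shortfall is d − 6, summing to 8 + 14 + 18 + 20 + 20 + 18 + 14 + 8 = 120 days. Mean 120/36 = 3.3 days in affected intervals and 120/225 = 0.5 day over all later intervals.
- The full 8 days: 1/225 = 0.4%.

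If every visit is on time, no interval is affected.

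**5. Whole-kit rounding.** Assume one strength at s sachets a day and unsplit kits. Kits = 90s/120 rounded up; days covered = 120 × kits / s.

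| Sachets/day | Days covered | Short of 98 days by |
|---|---|---|
| 1, 2, 3 | 120 | none |
| 4, 8, 12 | 90 | 8 |
| 5, 10 | 96 | 2 |
| 6 | 100 | none |
| 7 | 102.9 | none |
| 9 | 93.3 | 4.7 |
| 11 | 98.2 | none |

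Two illustrative fills (the IVR/IWR rules are not in the documents):
- 25 kg as 1, 1 and 2 sachets of 250 mg needs 4 × 90 = 360 sachets, exactly three kits, so every dose stops at day 90.
- 50 kg as 2 × 250, 2 × 250 and 1 × 1000 mg also needs exactly three 250-mg kits, but the single 1000-mg kit lasts 120 days. Morning and mid-day doses stop; the evening dose continues.

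**The case against.** The strongest reply is that Protocol 8.2.15 undertakes only to reduce the chance of shortages, so it states nothing false. That is fair as to wording. It does not dispose of the mismatch: Protocol 6.1.4 speaks of enough drug for each period, and 6 days is less than 7 on any reading.

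Several further objections stand and set the limits of the point.

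- **Eight days is conditional.** It needs opposite extremes at consecutive visits and no re-dispensing. Protocol 6.1.5 and 8.2.16 ask for sachets back for counting, while 6.1.7 places destruction or return to the sponsor after study completion. Carry-over is neither stated nor ruled out.
- **Not every patient would be wholly off drug.** Kit rounding covers some fills completely, and in the 50-kg example the evening dose remains available. Missed doses also stretch the supply; lost sachets shorten it.
- **A gap need not go unrecorded.** The visit itself is in window, but Protocol 11.4.3 plans to describe omissions and departures from planned therapy, Protocol 8.2.16 keeps an accountability log, and SAP 4.9 summarises compliance and interruptions. What is missing is a link from those records to the by-visit values.
- **Bias toward no effect is not shown.** A reader might infer it, but the study has no concurrent control and SAP 4.11.1 is descriptive. Under SAP 5.1, patients previously on ataluren would normally have an on-drug baseline, so losing drug effect would move them away from baseline. The documents do not say how quickly lung function or laboratory values change after dosing stops.
- **Trough results are now only listed.** SAP 4.12.5 and SAP 6 drop their summary, so the harm is to reading individual values.

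**Conclusion.** The mismatch is real and rests on the protocol's own numbers: 90 days of supply against in-window intervals of up to 91 days (first) and 98 days (later). The 1-day shortfall in the first interval holds whether or not returned sachets are re-dispensed. Shortfalls in later intervals, up to 8 days, require that they are not. The 7%, 16%, 3.3-day and 0.4% figures depend on the assumed uniform, independent timing and an exact 90-day fill.

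A reader might go further and infer that compliant patients commonly go 8 days without any ataluren, undetected, with lung-function and laboratory changes pulled toward zero. The documents do not support that. Eight days is the rare extreme, some fills leave part or all of the dosing covered, other records may show the omission, and the direction of any bias cannot be determined.

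This is a worthwhile and cheap correction affecting a minority of intervals. It does not undermine the safety analysis. SAP 2.1 records premature termination, so the dispensing change matters only for remaining dosing or for reuse of this protocol text.

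**What to change.** Reconcile supply length, visit window and return rule in Protocol 8.2.15, 6.1.5 and Table 3:

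- State whether counted, unused sachets are re-dispensed.
- If they are not, size each dispensing to the longest interval Table 3 permits, 98 days, plus a separate allowance for lost sachets. If they explicitly are, 91 days plus that allowance is enough.
- Carry the figure into the IVR/IWR dispensing rules. Dose and visit schedule stay as they are.

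Cost: 98/90 = 1.089, about 9% more drug per dispensing before the loss allowance (about 1% for 91 days), sometimes an extra kit, much of it returned unused. Otherwise it is a short text change and an IVR/IWR parameter.

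Optionally, amend the SAP before database lock to flag visits at which dispensed quantity and dates show that supply would have run out, and repeat the by-visit summaries without those values. The accountability records already required hold the data, so the cost is one derived flag and a sensitivity table.

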8.2.16. Study Drug Compliance

Study drug compliance will be assessed using a Subject Study Drug Accountability Log (to be completed by the investigational site pharmacist or delegate site staff), which will document the return of unused sachets for compliance assessments.

Patients or caregivers will return all unused sachets of study drug to the study site for full compliance assessments using the Subject Study Drug Accountability Log. Clinic staff will record the study drug dosing information including the actual clock time of each dose when the patient is dosed in the clinic.

8.2.17. Adverse Events

Adverse events must be assessed and documented at each clinic visit. This information will be collected at Screening/Baseline (Visit 1) – following initiation of study drug, Week 12 (Visit 2), Week 24 (Visit 3), Week 36 (Visit 4), Week 48 (Visit 5), Week 60 (Visit 6), Week 72 (Visit 7), Week 84 (Visit 8), Week 96 (Visit 9) and at the Post-Treatment Visit (4 weeks post discontinuation of study drug). In addition, patients/caregivers will be encouraged to report adverse events of concern at any time in the intervals between visits.

8.2.18. Concomitant Medications

Information regarding any concomitant medications administered, as well as information regarding all non-drug therapies, will be collected throughout the study. This information will be collected at Screening/Baseline (Visit 1) – following initiation of study drug, Week 12 (Visit 2), Week 24 (Visit 3), Week 36 (Visit 4), Week 48 (Visit 5), Week 60 (Visit 6), Week 72 (Visit 7), Week 84 (Visit 8), Week 96 (Visit 9) and at the Post-Treatment Visit (4 weeks post discontinuation of study drug).

8.2.19. Presence of Pseudomonas aeruginosa in Sputum

The results of standard-of-care sputum cultures obtained by each subject's treating CF physician will be collected throughout the study. Available data, including the presence of *Pseudomonas aeruginosa*, will be collected from each subject's treating CF physician at Week 12 (Visit 2), Week 24 (Visit 3), Week 36 (Visit 4), Week 48 (Visit 5), Week 60 (Visit 6), Week 72 (Visit 7), Week 84 (Visit 8), and Week 96 (Visit 9 - End-of-Treatment/Premature Discontinuation).

8.2.20. Spirometry

Lung function will be assessed by spirometry using standardized equipment and procedures (please refer to the Study Manual for detailed instructions). Spirometry will be performed at all study visits. Centralized review will be provided for all spirometry measurements.

Consistent with usual practice, it is important that all subjects withhold the following medications prior to spirometry testing in order to obtain an accurate assessment of baseline lung function:

- Short-acting beta agonists (SABAs) should not be administered within 4 hours prior to testing.
- Long-acting beta agonists (LABAs) should not be administered within 12 hours prior to testing.

Inhaled antibiotics prior to testing is permitted. If chronically used, and done for the baseline visit, the administration of inhaled antibiotic should be consistently administered before every study visit (as at the baseline visit).

Use of SABAs, LABAs, and inhaled antibiotic will be captured in the central spirometry vendor's system prior to start of testing.

In exceptional circumstances where the subject's lung function is too labile to tolerate the delay in the use of beta agonists, the investigator should confer with the PTC medical monitor to get approval to deviate from this requirement. In this instance, the subject should have all spirometry measurements performed after use of the prescribed beta agonist(s) at the appropriate interval(s).

8.2.21. Pulmonary Exacerbation Rate

Signs and symptoms associated with respiratory events that may constitute a pulmonary exacerbation will be collected and documented by the investigator or other qualified medical personnel on a Respiratory Event Form. This assessment will be conducted on Visit 1, Week 12 (Visit 2), Week 24 (Visit 3), Week 36 (Visit 4), Week 48 (Visit 5), Week 60 (Visit 6), Week 72 (Visit 7), Week 84 (Visit 8), and Week 96 (Visit 9 - End-of-Treatment/Premature Discontinuation), and at the time of any unscheduled contact between the patient and the clinic. In addition to patient/caregiver and investigator discussion at scheduled study visits, patients/caregivers are encouraged to contact their investigator by telephone with all pulmonary exacerbation details for any events that occur between scheduled visits.

8.2.22. CFQ-R

The CFQ-R will be administered prior to performance of other study procedures with the exception of obtainment of informed consent. The questionnaire will be administered at all study visits.

8.2.23. Blood for Analysis of Pharmacokinetics

Blood for trough ataluren concentrations will be collected at Week 24 (Visit 3), Week 48 (Visit 5), Week 72 (Visit 7), and Week 96 (Visit 9 - End-of-Treatment/Premature Discontinuation immediately prior to the morning dose of study drug. The Central Laboratory Manual should be consulted for collection, processing, and shipping details.

Samples will be stored at the bioanalytical lab for analysis of ataluren parent drug using a validated high performance liquid chromatography with tandem mass spectrometry (HPLC/MS-MS) method. Thereafter, samples will be retained at the bioanalytical lab for potential follow-up analyses of ataluren metabolites.

8.3. Blood Collection Summary

Every effort has been made to minimize blood drawing to the minimum required to monitor patient safety during the trial. Assuming a 96-week treatment period and all visits completed as noted in Table 3, the maximum amount of blood to be drawn at a visit is ~12 mL and the total amount of blood to be drawn over the entire 96-week study period (including the Screening visit, the 96-week treatment period, and the 4-week follow-up period) is approximately 112 mL.

9. ADVERSE EVENT ASSESSMENTS

9.1. Adverse Event Definitions

9.1.1. Adverse Events

An adverse event is any untoward medical occurrence associated with the use of a drug (investigational medicinal product) in humans, whether or not it is considered related to the drug. An adverse event can therefore be any unfavorable and unintended sign (including an abnormal laboratory finding), symptom, or disease in a study patient who is administered study drug in this study.

For this protocol, untoward medical occurrences that should be reported as adverse events include the following:

- All adverse events that are suspected or are not suspected to be due to study drug.
- Overdose (administration of a study drug dose >4 times the highest intended total daily dose level for this protocol [>160 mg/kg/day]) of study drug.
- All reactions from medication misuse, abuse, withdrawal, sensitivity, or toxicity.
- All reactions that result from medication errors or uses of the study drug outside what is described in the protocol.
- Apparently unrelated illnesses, including the worsening of a preexisting illness.
- Injury or accidents. Note that if a medical condition is known to have caused the injury or accident (a fall secondary to dizziness), the medical condition (dizziness) and the accident (fall) should be reported as 2 separate adverse events. The outcome of the accident (hip fracture secondary to the fall) should be recorded in source documents.
- Abnormalities in physiological testing or physical examination findings that require clinical intervention or further investigation (beyond ordering a repeat [confirmatory] test).
- Laboratory or ECG abnormalities that require clinical intervention or further investigation (beyond ordering a repeat [confirmatory] test) unless they are associated with an already reported clinical event. Laboratory abnormalities associated with a clinical event (eg, elevated liver enzymes in a patient with jaundice) should be captured in the source documents. Laboratory abnormalities not requiring clinical intervention or further investigation will be captured as part of overall laboratory monitoring, and should not be reported as adverse events.
- A pre-existing condition (eg, allergic rhinitis) must be noted on the appropriate CRF for Visit 1, but should not be reported as an adverse event unless the condition worsens or episodes increase in frequency during the adverse event reporting period. Diagnostic and therapeutic non-invasive and invasive procedures, such as surgery, should not be reported as adverse events. However, the medical condition for which the procedure was performed should be reported if it meets the definition of an adverse event. For example, an acute appendicitis that begins during the adverse event reporting period should be reported as the adverse event and the resulting appendectomy should be recorded in the source documents. If a surgical procedure was planned prior to entry into the study, and the surgery is not performed because of a worsening of a baseline condition, this should not be reported as an

adverse event. Note that, as described in Section 9.1.2, any inpatient hospitalization occurring as the consequence of an adverse event during the study period should be reported as an SAE.

Each adverse event is to be classified as serious or non-serious by the investigator using medical and scientific judgment.

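### Protocol 9.1.1 contradicts itself on injuries that follow a medically caused accident and on a worsening that cancels planned surgery, so some reportable terms may be missing from the primary safety tables

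*Protocol*

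**What the plan says.** Both passages are in Protocol 9.1.1.

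**Injuries.** The section opens its list with "untoward medical occurrences that should be reported as adverse events include the following", and injury or accidents is one of the items. A note then covers the case "if a medical condition is known to have caused the injury or accident". In its example, "the medical condition (dizziness) and the accident (fall) should be reported as 2 separate adverse events". For the third element it says "The outcome of the accident (hip fracture secondary to the fall) should be recorded in source documents".

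**Planned surgery.** A later item deals with pre-existing conditions and procedures. It begins by making a pre-existing condition reportable once it worsens or its episodes become more frequent. It then says that procedures are not adverse events but the underlying condition may be. It closes with surgery planned before study entry: "and the surgery is not performed because of a worsening of a baseline condition, this should not be reported" as an adverse event. The list earlier in 9.1.1 includes "Apparently unrelated illnesses, including the worsening of a preexisting illness".

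**Use of the data.** The primary endpoint (Protocol 3.3, SAP 2.3.1) is the type, frequency, severity, timing and relationship of any adverse event. SAP 4.10.1 tabulates subjects by system organ class, preferred term and worst grade, and adds exposure-adjusted rates from event counts. Both treatment-emergent definitions (Protocol 11.4.5.1, SAP 4.10.1) include events that worsen on treatment.

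**The concern.** A fracture after a fall is a new medical condition. It meets the general adverse event definition at the top of 9.1.1 and falls under the injury item. It may also be the most severe element of the episode. Yet the note counts two adverse events in the example and gives the fracture a different destination. A site that takes the note at its word would record no term, grade, relationship or outcome for it.

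The note applies where a medical condition led to the accident. Those are the cases in which a chain from a possibly drug-related symptom to an injury would be of most interest in a long-term safety study.

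The surgery sentence raises a similar problem. A deterioration serious enough to cancel an operation is clinically notable, and the sentence can be read as telling sites not to report it.

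**Working it through.** The plan states no figure on this point, so the check is textual, with one calculation for scale.

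**1. Does recording in source documents mean instead of the CRF?** The text does not say only. Protocol 9.1.1 uses the phrase in two other places:
- Laboratory abnormalities that accompany a clinical event are captured in source documents. They are excepted from separate reporting when that event has already been reported.
- In the appendicitis example, the illness "should be reported as the adverse event and the resulting appendectomy should be recorded in the source documents".

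In both places source documents are the alternative to an adverse event entry, and a site would naturally read the fracture sentence the same way. The cases differ in kind, however. Raised enzymes are a sign of a reported event and an appendectomy is a procedure, whereas a fracture is a condition in its own right.

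**2. Do other rules restore the injury's term?**
- Protocol 9.3 sends every adverse event to both source documents and CRF. That helps only if the site already regards the fracture as an adverse event, and 9.1.1 is where the site looks to decide that.
- Protocol 9.1.1 and 9.1.2 make a hospitalization resulting from an adverse event serious. The reported event is then the fall, and 9.9 requires the same term on the adverse event and SAE forms.
- Table 6 in 9.9 has source documents supplied on request for serious events and events of special interest. It gives no such route for a non-serious injury.
- Protocol 9.1.2 requires a death to be reported under the event that caused it, so a fatal injury would be named.
- SAP 4.1 builds listings from CRF modules, and SAP 4.10.1 builds tables from preferred terms and grades. An injury held only in source documents reaches neither.

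The episode therefore survives, but apart from a fatal case the injury's own term, grade and relationship need not.

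**3. What does the surgery sentence exempt?** Its pronoun has two possible referents:
- *The cancelled operation.* This fits the preceding sentences on procedures and conflicts with nothing.
- *The worsening.* This conflicts with the item on worsening of a pre-existing illness, with the opening of the same item, and with both treatment-emergent definitions.

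The wording does not decide between them. The sentence may also be a slip for surgery that was carried out, and not because of a worsening, but the documents do not confirm this.

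**4. Scale.** The documents give no rate of medically caused accidents, resulting injuries or cancelled operations. The effect of one unrecorded subject on a preferred-term percentage is 1/N:
- N about 200 (Protocol 5.1): 1/200 = 0.5 percentage points.
- N at most about 279 (the upper bound in SAP 2.4): 1/279 = 0.36 percentage points.

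These are effects per subject and do not estimate how many subjects are affected.

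**The case against.** The strongest reply is that 9.1.1 is ambiguous and does not instruct sites to omit anything. Source documents and CRF are not mutually exclusive under 9.3, injury is on the reportable list, and the general definition covers a fracture. The note is confined to accidents with a known medical cause, so other injuries fall under the unqualified item. Even within the note, the symptom and the accident each carry a grade, relationship, outcome and seriousness, 9.5 asks for the highest grade attained in each episode, and hospitalization brings SAE reporting. On surgery, several rules require a worsening to be reported, against one unclear pronoun. Finally, SAP 2.1 puts early termination at 2 March 2017 and the SAP is dated 14 July 2017, so rewriting the protocol cannot change data already collected.

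Most of this stands, and it limits the point. A reader might infer that the plan removes real adverse events from the safety tables by instruction, or that whole episodes vanish. The documents support neither inference: what happens depends on which sentence a site follows, and the symptom and fall are captured in any case.

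The reply does not remove the contradiction. The specific note is the text a site would apply to a fracture, and nothing else in the protocol says that a non-fatal resulting injury gets its own entry. Grading the fall more severely would not supply the fracture's term. A worsening that one sentence appears to exempt and others require is likely to be handled differently across sites.

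**Conclusion.** Section 9.1.1 is internally inconsistent on two points that feed the primary endpoint. For accidents with a known medical cause, the resulting injury's preferred term, grade and relationship may be absent from the treatment-emergent tables, although the episode appears through its cause and the accident. For planned surgery cancelled because of a worsening, the worsening itself may go unreported.

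The size is unknown. One unrecorded subject is worth about 0.36 to 0.5 percentage points of a preferred term over the patient numbers above, and any total would be an assumption.

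The conclusion assumes that at least some sites read the fracture note as an alternative to CRF entry, as its parallels in 9.1.1 suggest, or read the surgery sentence as covering the worsening. If every site followed the general rules instead, nothing would be missing. The point deserves correction because it touches the primary safety data and is cheap to settle, but it is not evidence that events have been lost.

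**What to change.** In Protocol 9.1.1, or in CRF completion guidance if the protocol is no longer being amended:
- End the injury note by stating that the resulting injury is also entered on the CRF as an adverse event, with its own grade, relationship and seriousness.
- Reword the surgery sentence so that only the planned or cancelled procedure is exempt, and any worsening of the baseline condition in the reporting period is an adverse event.

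Because the study ended early, the step that can still affect the results is a targeted query before database lock. For each reported fall or accident, sites check source documents for an injury not entered on the CRF. Sites also identify any pre-planned surgery cancelled because of a worsening and confirm that the worsening was reported. The study report should state what the query found. If the database is already locked, it should state the limitation instead.

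The cost is two sentences, a limited site query and slightly higher adverse event counts. No SAP analysis changes, since added events flow into the existing tables.
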